## 7 General Analysis Considerations

All demographic and baseline variables will be summarized by means, standard deviations, medians, and interquartile ranges (IQR) for continuous measures. Frequency and percentages will be reported for all categorical measures (including binary measures).

The general approach for statistical inference for aims associated with outcomes measured at multiple periods will utilize a mixed-effects multi-period crossover model with 2 blocks and 2 treatment periods per block (of length 6 weeks). Maximum likelihood estimation will be used primarily for parameter estimation and likelihood ratio tests will be used to test hypotheses under the primary and secondary objectives. Significance of an active treatment effect versus placebo will be determined by testing if the treatment effect coefficient differs from zero in the mixed-effect model. When there is a possibility of carryover effects, the multi-crossover model will incorporate carryover effect terms. Only carryover effects from active to placebo will be formally modelled. For outcomes recorded only at baseline and week 24, an appropriate generalized linear model will be used to estimate and test for the active treatment effect, controlling for covariates noted below and also the baseline value of the outcome.

All hypothesis tests will be two-sided using  $\alpha = 0.05$  significance level, and  $p$ -values unadjusted for multiple testing will be reported. The justification for this decision is that this is Phase II investigation and all assessed outcomes are of specific and unique interest. Much more important than testing hypotheses is the efficient estimation of all quantities of interest, and this will be carried out throughout the analyses. Treatment effect point estimates with 95% confidence intervals will be reported along with estimates of other model parameters, regardless of whether the null hypotheses were rejected or not.

The secondary and exploratory analyses proposed here are contingent on sufficient data availability after database lock. If the data for any outcome is insufficient for the proposed analysis, then the analysis that will be performed will be considered exploratory in nature. If data is insufficient to fit complex models in these cases (e.g., due to singularities or convergence issues), then the model will be simplified as necessary, e.g., fitting the model without the site random effect if that solves convergence or singularity issues. If this does not solve the problem, then summary statistics will be reported for the outcome in order to compare the active treatment to the placebo treatment.

[figure not shown]

Figure 2: Power versus Cohen's  $d$  effect size.  $B/W$  indicates the ratio of between-subject to within-subject variance of the WOMAC-A measure. The proposed sample size is  $n = 55$ . With 15% dropout per treatment period, there will be  $n = 29$  patients with complete observations at all treatment periods of this multi-crossover design. Assuming that only data from completers will be used in the analysis gives a lower bound of the power that can be achieved for the given range of effect sizes.

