At Baseline and Week 6, 12, 18, and 24/ET visits, 8.5 ml blood samples will be drawn. Serum will be separated and a commercially-available multiplex assay (the Myriad Human Inflammation MAP® 1.0) will be used to evaluate multiple inflammatory markers. In addition, we will assess:

- Monocyte chemoattractant protein-1 (MCP-1)/CCR-2 receptor binding inhibition by CNTX-6970 (Baseline and Weeks 6, 12, 18 and 24).
- Synovial fluid levels of cytokines and chemokines, assessed at the end of the first treatment period (Visit 3).
- Monocyte chemoattractant protein-1 (MCP-1)/CCR-2 receptor binding inhibition by CNTX-6970 in synovial fluid, assessed at the end of the first treatment period (Visit 3).

Extra (left over) blood samples not required to be sent to the lab for analysis will be frozen and batch shipped to NYU biobanking for future exploratory analysis. IF A SUBJECT HAS OPTED OUT OF SPECIMEN SAMPLING DO NOT SEND. See MOP for additional details.

An optional synovial fluid tap will be conducted on the index knee on subjects at the week 6 clinic visit. The synovial fluid tap is optional for both sites and participants. Approximately 1ml of synovial fluid will be withdrawn for biomarker analysis. Synovial fluid collection will be performed by a physician with training and experience. Synovial fluid analysis will include cytokines and chemokines as a part of establishing biomarker for treatment of OA pain with CNTX-6970.

Extra (left over) Synovial fluid from the sample that is not required to be sent to the lab for analysis will be sent to NYU biobanking for future exploratory analysis. IF A SUBJECT HAS OPTED OUT OF SPECIMEN SAMPLING DO NOT SEND.

F.2.2.1. Blood Test for Pharmacokinetics (PK analysis at Weeks 6, 12, 18, and 24/ET [V3, V5, V7 and V9])

Four (4) ml of Blood will be drawn. Pharmacokinetic/pharmacodynamics PK/PD analysis of this study will be conducted to determine dose relationship of CNTX-6970 and its analgesic effect in patients with OA. This determination will be obtained at the time when patients are at the steady state of CNTX-6970. Pharmacokinetic samples will be obtained at Week 6, Week 12, Week 18, and Week 24/ET Visits.

Extra (left over) blood samples, beyond what was required to be sent to the lab for analysis, will be frozen and batch shipped to NYU biobanking for future exploratory analysis. IF A SUBJECT

HAS OPTED OUT OF SPECIMEN SAMPLING DO NOT SEND. See MOP for additional details.

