A patient who remains in the study for the first two treatment periods or for all four treatment periods will receive a balanced exposure to treatments randomized to receive. If patients discontinue treatment prior to completing the entire 24 weeks of study, all their data (including weekly assessments) from their time in the study will be used in the analyses. Because the main analysis is based on maximum likelihood estimation using a mixed-effects multi-period crossover model, the inferences will be unbiased under missing at random assumptions. No imputation of missing data is planned for this study, unless intensive investigations indicate that reliable and valid data imputation is possible, in which case multiple imputation will be performed and the analysis of the imputed data sets will serve as a sensitivity check of the results from the primary analysis based on the mixed-effects models (van Buuren et al, 2011).

All analyses will adjust for age, sex, K-L grade, and site.

All hypothesis tests will be two-sided using 5% significance level, and *p*-values unadjusted for multiple testing will be reported. The justification for this decision is that this is a Phase II investigation and all assessed outcomes are of specific and unique interest. Much more important than testing hypotheses is the efficient estimation of all quantities of interest, and this will be carried out throughout the analyses. Point estimates, 95% confidence intervals and standardized effect sizes (e.g., Cohen's *d*) will be reported for all estimated effects, regardless of whether the null hypotheses were rejected or not.

K.2. Hypothesis testing

Aim 1: Assess the safety of CNTX-6970 (300mg BID).

There will be no formal hypothesis testing under Primary Study Aim 1. All AEs and SAEs observed during different treatment periods will be summarized based on severity and relation to the active treatment (CNTX-6970 300mg BID). The reports will include tabulation of the AEs and SAEs by period, block, and treatment; point estimates and 95% CIs will be reported. Similarly, we will summarize relevant laboratory measures (see Section F.2.1) with appropriate estimates.

Aim 2: Assess the efficacy of CNTX-6970 (300mg BID) in comparison to placebo with respect to the primary outcome measure for pain due to osteoarthritis of the knee - WOMAC Part A.

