Appendix II: Cytokines & Chemokines (from the Inflammation MAP Multiplex panel):

Adiponectin	Interleukin-23
Alpha-1-Antitrypsin	Interleukin-3
Alpha-2-Macroglobulin	Interleukin-4
Apolipoprotein(a)	Interleukin-5
Beta-2-Microglobulin	Interleukin-6
Brain-Derived Neurotrophic Factor	Interleukin-7
C-Reactive Protein	Interleukin-8
Complement C3	Macrophage Inflammatory Protein-1 alpha
EN-RAGE	Macrophage Inflammatory Protein-1 beta
Eotaxin-1	Matrix Metalloproteinase-3
Factor VII	Matrix Metalloproteinase-9
Ferritin	Monocyte Chemotactic Protein 1
Fibrinogen	Myoglobin
Granulocyte-Macrophage Colony-Stimulating Factor	Plasminogen Activator Inhibitor 1
Haptoglobin	Pulmonary and Activation-Regulated Chemokine
Immunoglobulin A	Serum Amyloid P-Component
Immunoglobulin M	Stem Cell Factor
Intercellular Adhesion Molecule 1	T-Cell-Specific Protein RANTES
Interferon gamma	Thyroxine-Binding Globulin
Interleukin-1 alpha	Tissue Inhibitor of Metalloproteinases 1
Interleukin-1 beta	Tumor Necrosis Factor alpha
Interleukin-1 receptor antagonist	Tumor Necrosis Factor beta
Interleukin-10	Tumor necrosis factor receptor 2
Interleukin-12 Subunit p40	Vascular Cell Adhesion Molecule-1
Interleukin-12 Subunit p70	Vascular Endothelial Growth Factor
Interleukin-17	Vitamin D-Binding Protein
Interleukin-18	von Willebrand Factor
Interleukin-2	

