**Aim 5:** Assess the effect of CNTX-6970 (300mg BID) in comparison to placebo with respect to biomarkers of pain and inflammation: (a) Staircase-Evoked Pain Assessment; (b) serum and synovial fluid levels of chemokines and cytokines; and (c) synovial monocyte chemoattractant protein-1/CCR-2 receptor binding inhibition in blood and synovial fluid.

**HYPOTHESIS 4:** Compared to placebo, CNTX-6970 300mg BID will result in greater improvement with respect to (a) Staircase-Evoked Pain Assessment; (b) serum and synovial fluid levels of chemokines and cytokines; and (c) synovial monocyte chemoattractant protein-1/CCR-2 receptor binding inhibition in blood and synovial fluid.

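### Hypothesis 4(b) leaves a 55-analyte commercial panel under unadjusted 5% testing, with no analyte prioritised: about 2.75 false positives expected in synovial fluid if none responds, more only if serum is tested the same way

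*SAP*

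**What the plan says.** **Testing rule.** Protocol K.1 states "All hypothesis tests will be two-sided using 5% significance level", and SAP section 7 adds that p-"values unadjusted for multiple testing will be reported". The reason given is that "this is Phase II investigation and all assessed outcomes are of specific and unique interest". The SAP goes straight on: "Much more important than testing hypotheses is the efficient estimation of all quantities of interest". It promises estimates and 95% intervals whether or not a null hypothesis is rejected.

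**Hypothesis.** Hypothesis 4, a secondary hypothesis under Aim 5, claims greater improvement on CNTX-6970 than on placebo. Part (b) concerns "serum and synovial fluid levels of chemokines and cytokines".

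**Panel.** Protocol F.2.2 says "a commercially-available multiplex assay (the Myriad Human Inflammation MAP® 1.0) will be used to evaluate multiple inflammatory markers". The analytes are listed under "Appendix II: Cytokines & Chemokines (from the Inflammation MAP Multiplex panel", and SAP 4.4.3 refers to the protocol appendix list for both fluids. Neither document ranks the analytes, gives an expected direction for any of them, or defines a composite or global test.

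**Planned analysis.** Protocol K.2 analyses all of Hypothesis 4 by the Aim 3 approach. SAP 9.2 separates the fluids. Synovial measures at week 6 are regressed on first-period treatment, with hypothesis testing as in Aim 4. Serum is given a mediation analysis of WOMAC-A change, with methods that the SAP says do not yet exist. No per-analyte treatment-effect test is written there for serum.

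**The concern.** Declining to adjust is a coherent choice when each outcome was picked because its own answer matters. An off-the-shelf panel is a different object. It includes MCP-1 and RANTES, the ligands of the receptors the drug blocks, but also myoglobin, thyroxine-binding globulin, factor VII and vitamin D-binding protein. Neither document says why those are of interest in their own right. With 55 analytes under one formal hypothesis and no rule for what counts as support, a handful of results below 0.05 could be reported as positive secondary findings even if the drug changed nothing. What is at stake is the reading of the Aim 5 biomarker results, not the efficacy conclusion.

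**Working it through.** The plan states no number of tests, no expected number of false positives and no familywise error rate, so there is no figure of its own to reproduce.

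**Inputs**
- Per-test level: 0.05, two-sided, unadjusted (protocol K.1, SAP 7).
- Panel size: 28 + 27 = 55, counted from the two columns of protocol Appendix II, which prints no total. The match with the sample size of 55 is a coincidence.
- Fluids: synovial (tests written in SAP 9.2) and serum (tests implied by protocol K.2 only).
- Assumptions, not in the documents: one test per analyte per fluid; no analyte responds (relaxed in step 3); a common correlation of 0 to 0.7 between test statistics.

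**1. Expected false positives** = number of true-null tests × 0.05. This needs no independence.
- Synovial only: 55 × 0.05 = 2.75.
- Both fluids: 110 × 0.05 = 5.5.

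**2. Chance of at least one.** Under independence this is 1 − 0.95^m. For correlated statistics it comes from 100,000 simulated draws of equicorrelated normals.

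| Assumed correlation | Synovial, m = 55 | Both fluids, m = 110 |
|---|---|---|
| 0 | 94.0% | 99.6% |
| 0.3 | about 83% | about 95% |
| 0.5 | about 65% | about 80% |
| 0.7 | about 42% | about 51% |

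Correlation leaves the expected count alone but makes the hits cluster. For synovial fluid at 0.7, a trial with any false positive has on average 2.75 / 0.42 ≈ 6.5 of them, against 2.75 / 0.94 ≈ 2.9 under independence.

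**3. If some analytes do respond.** With 50%, 70% or 90% of analytes truly null, the expected count is:
- synovial only: 55 × 0.05 × share = 1.4, 1.9 or 2.5;
- both fluids: 110 × 0.05 × share = 2.75, 3.85 or 4.95.

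So 2.75 and 5.5 are ceilings for their respective test counts.

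**The case against.** Several points on the other side have force.

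- **The SAP does not write 110 tests.** A reader might infer from Hypothesis 4 that both fluids go through 55 tests each, giving 5.5 false positives. SAP 9.2 does not support that. The SAP's change history shows the mediation proposal entering in version 5.2 of July 2024, after protocol version 9.0 of January 2024. The serum count rests on protocol K.2, or on applying SAP 7's general rule for repeatedly measured secondary outcomes to serum. This stands, and it is why 2.75 is the figure to use.
- **One test per analyte is inferred.** Hypothesis 4 speaks of levels collectively. This stands as an assumption, although neither document offers another construction.
- **Some analytes may respond.** The panel contains the ligands of the drug's own targets. This stands; step 3 of the working shows the effect.
- **The synovial tests may never be run as planned.** The tap is optional for sites and participants and is done once. SAP 7 makes an analysis exploratory if data are insufficient, and falls back to summary statistics if simpler models also fail. This stands, but the safeguard depends on sparse data, not on the size of the panel.
- **Estimation is ranked above testing.** True, and full reporting would let a reader compute an adjustment. But the tests and p-values remain, and unadjusted 95% intervals exclude zero for about 5% of null analytes, so the emphasis does not remove the problem.

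A reader might also infer that chance hits under Aim 5 would pass into the biomarker search of Aim 7. No text says that Aim 5 p-values select Aim 7 features, and Aim 7 carries its own caveats: exploratory status, internal cross-validation (protocol K.3) and independent validation. That inference should not be drawn. Those caveats are, however, attached to Aim 7 and not to Aim 5.

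**Conclusion.** The point holds in a limited form. The stated reason for not adjusting does not fit a 55-analyte commercial panel in which nothing is prioritised, and Hypothesis 4(b) has no rule for calling an analyte changed beyond an unadjusted 5% test. From the SAP's own analysis text, about 2.75 false positives are expected in synovial fluid, assuming one test per analyte, enough samples to test, and no true effects. At least one is near certain only if the statistics are close to independent; at strong correlation the chance falls below one half. The figure of 5.5 applies only if serum is also tested per analyte, a matter on which the protocol and SAP differ. This is an inexpensive improvement to a secondary biomarker analysis. The single primary WOMAC-A test is untouched.

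**What to change.** 1. For every per-analyte treatment test under Hypothesis 4(b), report Benjamini-Hochberg q-values within each fluid beside the raw p-values, and call an analyte changed only if q is below a level stated in the SAP before unblinding. Keep all estimates, intervals and raw p-values.
2. Reconcile protocol K.2 with SAP 9.2 on whether serum analytes receive a treatment-effect test. If they do, write the model and apply the same rule within serum. If they do not, say so.
3. Leave all other outcomes unadjusted as planned.

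**Cost.** The synovial rule is one SAP sentence; settling the serum analysis takes more. Some nominal hits will no longer be called. As an illustration, if the q level were 0.05, an analyte standing alone among 55 would need a raw p of about 0.05 / 55 = 0.00091, which is demanding for an optional, single sample. The level is therefore worth choosing deliberately. No extra patients, samples or visits are needed.

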## 7.1 Timing of Analyses

There are no planned interim analyses for this trial. The final analysis will occur when the study finishes (after data lock).

## 7.2 Analysis Populations

This study is designed to evaluate changes in pain related to primary OA of the knee using an ITT principle. Eligible subjects will have evidence of chronic knee OA with a history of moderate to severe pain in the designated index knee for a minimum of 6-months prior to screening. Although this condition commonly affects multiple joints and subjects may have bilateral OA of the knee(s), the efficacy assessments will be conducted only on the index knee.

### 7.3 Covariates and Subgroups

All analyses will adjust for K-L grade, age, sex, and site (as a random effect if the data is sufficient to model a site random effect).

### 7.4 Missing Data

A patient who remains in the study for the first two treatment periods or for all four treatment periods will receive a balanced exposure to both treatments. Because the main analysis is based on maximum likelihood estimation using a mixed-effects multi-period crossover model, the inferences will be unbiased under missing at random (MAR) assumptions. No imputation of missing data is planned for this study, unless intensive investigations indicate that reliable and valid data imputation is possible, in which case multiple imputation will be performed and the analysis of the imputed data sets will serve as a sensitivity check of the results from the primary analysis based on the mixed-effects models (van Buuren and Groothuis-Oudshoorn, 2011).

If a patient discontinues treatment prior to completing the entire 24 weeks of study, all their data (including weekly assessments) from their time in the study up to time of discontinuation will be used in the analyses.

Should a patient discontinue study medication and decide to withdraw consent, an end of study visit should be scheduled at the next of the closest following clinic visit. Should a patient discontinue study medication, but not withdraw consent, best efforts will be made by the site to collect all study data at the regular study assessment times through the next of the closest following clinic visits. At this clinic visit, all assessments outlined for the end of study visit should be conducted. For subjects who continue to be followed for safety to the end of the period, adverse events should continue to be reported.

### 7.5 Interim Analyses and Data Monitoring

No interim analysis is planned for this study.

## 8 Safety Analyses

A primary objective of this trial is to evaluate the safety of CNTX-6970 300 mg BID for the treatment of pain related to OA of the knee compared to placebo. The primary safety endpoint is the incidence of treatment emergent adverse events (TEAEs), reported between the administration of study drug on Day 1 and the completion of the study at Week 24.

**Aim 1:** Assess the safety CNTX-6970 (300 mg BID).

There will be no hypothesis testing under Aim 1. All AEs and SAEs observed during different treatment periods will be summarized based on severity and relation to the active treatment (CNTX-6970 300mg BID). The reports will include tabulation of the AEs and SAEs by period, block, and sequence; point estimates and 95% CIs will be reported. Similarly, we will summarize relevant laboratory measures which include chemistry and Complete Blood Count (CBC) with appropriate estimates.

The primary safety endpoint is the incidence of treatment emergent adverse events (TEAEs), reported between the administration of study drug on Day 1 and the completion of the study at Week 24 or Early Termination. Specifically, the primary safety endpoint for the study is the following: Percent of adverse events and serious adverse events in the final 2 weeks of each treatment period. Vital signs (heart rate, blood pressure, etc.) will be obtained regularly throughout the study at the time of study visits. Height and weight will be collected during the screening period and at the subject's final study visit. Blood chemistry and hematology panels will also be obtained regularly at study visits. All ECGs will be documented by recording date, time, heart rate, QRS duration, PR interval, RR interval, QT, and QTcF on the eCRF. Paper strips will be maintained in the patient file. If indicated, additional ECG assessments can be made at the discretion of the investigator.

The severity of each AE will be graded on a 4-point scale and reported in detail as indicated on the eCRF. Vital signs, systemic effects, and laboratory abnormalities will be graded using the Toxicity Grading Scale

for Healthy Adult and Adolescent Volunteers Enrolled in Preventive Vaccine Clinical Trials, available at <https://www.fda.gov/media/73679/download> (See MOP Appendix M).

- Grade 1 (Mild: No interference with activity)
- Grade 2 (Moderate: Some interference with activity, not requiring medical attention)
- Grade 3 (Severe: Prevents daily activity and requires medical intervention)
- Grade 4 (Potentially Life Threatening: Emergency Room visit or hospitalization).

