In rat models of pain varied with the model and was achieved in the dose range of 1 to 30 mg/kg. In models of inflammatory or neuropathic pain, the minimum effective doses were in the range of 1 to 10 mg/kg.

No relevant off-target pharmacological effects have been identified within the effective dose range. There was no evidence of a proarrhythmic risk of CNTX-6970 based on human Ether-à-go-go-related gene or papillary muscle studies. QTc prolongation was reported in the monkey at 250 mg/kg, but not at 50 mg/kg (maximum plasma concentration [Cmax] 5.67 µg/ml).

CNTX-6970 is a moderate clearance compound (17 to 34 ml/min·kg) with a high volume of distribution in rats and monkeys (4 to 6 L/kg). Oral bioavailability was high in female rats (95%) and monkeys (62%) and moderate in male rats (34%).

CNTX-6970 shows a moderate to low (~67 to 89%) binding to mouse, rat, cynomolgus monkey, and human plasma proteins.

CNTX-6970 was predominantly metabolized by CYP2C9 with a minor contribution of CYP3A4. Drug-drug interactions (DDIs) resulting from inhibition of transporters or cytochrome P450s (CYPs) are unlikely to occur in humans; the mean Cmax in humans after a single oral dose of 300 mg is at least 30-fold lower than the half maximal inhibitory concentrations for the transporters studied and the Ki for CYP2C9 inhibition (Ki = 29.9 µM).

In rats, CNTX-6970 was the dominant drug-related species in plasma, urine, feces, and bile. The major route of excretion for parent and metabolites was via bile and feces; urinary excretion only accounted for 9 to 18% of the administered dose.

In male and female rats, CNTX-6970 (20 mg/kg, 75 mg/kg, or 300 mg/kg) was given orally once daily (QD) for 4 weeks to assess toxicity and reversibility (4 weeks). At 300 mg/kg, gastric erosions and gastroesophageal reflux with lesions in the upper respiratory tract were considered related to the irritant potential of the test article. Foam cell aggregates (consistent with phospholipidosis) were identified in the gastrointestinal tract, liver, lungs, and mesenteric lymph nodes at 300 mg/kg. These changes were fully reversible with the exception of foam cell aggregates in the lungs of females. The NOAEL was 75 mg/kg where the mean Cmax was 3.97 and 6.61 µg/ml in males and females, respectively, and the mean area under the plasma concentration time curve (AUC) to the 24-hour time point (AUC0-24hr) was 15.8 and 32.6 µg·hr/ml in males and females, respectively, on Day 28.

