 - If positive, the subject will have the opportunity to provide evidence of medical necessity for their result, e.g. positive for oxycodone due to prescribed intermittently for their OA pain. The Medical Monitor will make the final decision regarding medical support for any positive results.
 - For this study, continuing intermittent opioid use is allowed as a rescue analgesic medication. See Appendix III and MOP for additional information.
 - For this study, medical marijuana (or equivalent) use is allowed for use depending on regional legality.
3. ECG: 12-lead ECGs will be measured at all in-clinic visits.
 - All ECG tracings should be checked for completeness and potential artifacts during the visit. If poor quality or otherwise indicated, additional ECG assessments can be made at the discretion of the investigator.
 - All ECG tracings will be uploaded to ERT (central ECG laboratory) and read at the scheduled time points by a central reader. The site will download the ECG report results from the ERT portal.
 - An investigator at the site is required to review all ECG reports to assess for potential safety concerns or exclusionary reasons. Any abnormalities noted by the central reader must be assessed by the Investigator for clinical significance (CS/NCS) on the report with a date and signature or initials:
 - Abnormal and Not Clinically Significant (NCS)
 - Abnormal and potentially Clinically Significant (CS)

- Any ECG results that are judged by the Investigator to be potentially CS will be recorded on the ECG report and the eCRF. This would constitute an AE and should be entered on the Adverse Event Form and monitored as described in Section F.4.8.1 Adverse Event Reporting. Repeat or unscheduled samples may be taken for safety reasons or to address technical issues with the samples.
- The site will upload the report with the investigator's signature and assessment to Florence within 3-business days of receipt of the ERT report. If technical issues arise, please refer to the ERT manual for other methods of transmission. See **MOP Appendix AC. Investigator Source Expectations and DDE Expectations** for investigator requirements.

4. **Clinical Blood Lab Tests:** Chemistry will be obtained at each in-clinic visit. Hematology will be obtained at the Screening Visit, and at the Weeks 6, 12, 18, and 24/ET Visits.

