F.3.1.1. Automatic Stopping Criteria for Subjects

If a subject meets any of the following criteria at any time during the study, they must be discontinued from the study drug and withdrawn from participation, in accordance with the procedures outlined in Section F.3.2.

- a. 1) ALT and/or AST $>3x$ ULN with total bilirubin $>2x$ ULN (unless elevated bilirubin is related to confirmed Gilbert's Syndrome). Subjects with total serum bilirubin $>2x$ above ULN will be followed until resolution. 2) Confirmed AST and/or ALT $>5x$ ULN for more than 2 weeks.
- b. Serum creatinine $>1.5 \times$ ULN or Grade 2 (moderate) value based on Toxicity Grading Scale for Healthy Adult and Adolescent Volunteers Enrolled in Preventive Vaccine Clinical Trials.

- c. ECGs (minimum criteria): absolute QTcF \geq 500 ms; absolute QTcF $<$ 320 ms (clinically significant QTc shortening); prolongation in repeated, averaged ECG measures of PR or QRS of $>$ 40 ms from the Baseline Visit.
- d. Monocyte count $<$ 1% of white blood cells (e.g., for WBC = 4,500/ μ L, stop if monocyte count $<$ 0.01 * 4,500 or 45/ μ L), hemoglobin $<$ 11 g/dL (Grade 2 in females) or $<$ 12.4 g/dL (Grade 2 in males), platelets $<$ 100,000/ μ L on 2 consecutive blood draws. A confirmatory blood draw will be completed at an in-clinic unscheduled visit. Discontinuation will be confirmed by the consecutive blood draw at the next in-clinic visit.

F.3.2. Discontinuation of Subjects who Stopped taking Study Medication

Should a patient discontinue study medication and decide to withdraw consent, an EOS visit should be scheduled at the earliest convenience to complete the EOS study procedures, unless the subject agrees to schedule it for the next study visit.

Should a patient discontinue study medication, but not withdraw consent, best efforts should be made by the site to collect all study data at the regular study assessment times through the closest of the following study visits: Week 6, Week 12, Week 18 or Week 24/ET. At this clinic visit, all assessments outlined for the EOS visit should be conducted.

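### The SAP plans no group-level summary of ECG data, and none of vital signs beyond graded AEs, so no drug-versus-placebo QTcF estimate would result

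*SAP*

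**What the plan says.** Collection is thorough. Protocol F.2.1, item 3, states that "12-lead ECGs will be measured at all in-clinic visits", with central reading, and the Schedule of Events places them at Screening, Baseline and Weeks 3, 6, 9, 12, 15, 18, 21 and 24. Vital signs are taken at Screening, Baseline and Weeks 6, 12, 18 and 24.

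Analysis is thin. SAP Section 8 plans AE and SAE tabulations with point estimates and 95% CIs, and then "we will summarize relevant laboratory measures which include chemistry and Complete Blood Count (CBC) with appropriate estimates". Its ECG sentence, shared with Protocol F.2.7, reads "All ECGs will be documented by recording date, time, heart rate, QRS duration, PR interval, RR interval, QT, and QTcF on the eCRF". It describes data capture. For vital signs, Section 8 says that they are obtained at visits and that abnormalities are graded on the toxicity scale.

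Protocol K.2, Aim 1, is slightly wider: "we will summarize relevant laboratory measures (see Section F.2.1) with appropriate estimates".

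Two routes bring an ECG finding into the results. The first is clinical judgement on a tracing (F.2.1): "Any ECG results that are judged by the Investigator to be potentially CS will be recorded on the ECG report and the eCRF", which makes it an AE. The second is individual discontinuation under F.3.1.1(c), which uses absolute QTcF limits (at or above 500 ms, below 320 ms) and PR or QRS prolongation of more than 40 ms from Baseline in repeated, averaged measures.

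On prior evidence, Protocol A.1 says "QTc prolongation was reported in the monkey at 250 mg/kg, but not at 50 mg/kg" and, just before that, "There was no evidence of a proarrhythmic risk of CNTX-6970" in the hERG and papillary muscle studies.

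**The concern.** The trial measures QTcF, PR, QRS and heart rate repeatedly on drug and on placebo in the same patients, then plans nothing that compares them by treatment. Prior repeat-dose experience in people is 10 days in healthy volunteers (Protocol A.2.2 and Section C). This trial gives patients aged 40 to 90 two 6-week periods on drug. A report that lists few or no ECG-related AEs could be taken to show no effect on repolarisation when that effect was never estimated. Choosing ECG metrics only after unblinding would also invite the question of why those were chosen.

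**Working it through.** **Could any text already supply the analysis?**

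- The SAP says laboratory measures and names chemistry and CBC. An ECG is not a laboratory measure.
- Protocol K.2 points to F.2.1, whose title covers laboratory and diagnostic procedures and which lists ECG (item 3) and vital signs (item 5). But the sentence still says laboratory measures, Table 2 in F.2.1 omits both, and the SAP, which postdates the protocol, names chemistry and CBC only.
- No other SAP section mentions observed ECG values, change from Baseline, a treatment contrast or threshold counts.

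**What the design offers.** The sequences are DPPD and PDDP (SAP 5.3), with ECGs at Weeks 3 and 6 of each period. A completer therefore has 4 ECGs on drug and 4 on placebo. The SAP's completer count reproduces: 55 × 0.85⁴ = 28.7, stated as about 29. That gives 29 × 4 = 116 tracings per treatment. Carryover should not rule out the Week 3 ECGs: K.2 gives a half-life of 15.8 to 16.6 hours, and 3 weeks is 504 hours, so 504/16.6 = 30 to 504/15.8 = 32 half-lives.

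**Precision of a QTcF difference.** The documents give no QTcF SD, so a within-patient visit-to-visit SD of 8, 10 or 15 ms is assumed. With r ECGs per treatment per patient, half-width = 1.96 × SD × √(1/r + 1/r) / √n. For n = 29:

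| SD (ms) | r = 4 | r = 2 (end of period only) |
|---|---|---|
| 8 | 2.06 | 2.91 |
| 10 | 2.57 | 3.64 |
| 15 | 3.86 | 5.46 |

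Example: 1.96 × 8 × √0.5 / √29 = 2.06 ms. The r = 4 column treats a patient's ECGs as independent given the patient. Neither column allows for variation between patients in the drug effect.

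**What the 500 ms limit shows of a 10 ms mean shift.** Two assumed QTcF distributions (mean and SD also not in the documents), normal tails:

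- Mean 420, SD 20: z falls from 4.0 to 3.5, so P(≥500) rises from 0.00003 to 0.00023. Expected on-drug tracings: 116 × 0.00023 = 0.03.
- Mean 430, SD 25: z falls from 2.8 to 2.4, so P rises from 0.0026 to 0.0082. Expected tracings rise from 116 × 0.0026 = 0.30 to 116 × 0.0082 = 0.95. The chance of at least one is 1 − (1 − 0.0082)¹¹⁶ = 62% if tracings are independent, or 1 − (1 − 0.0082)²⁹ = 21% if a patient's tracings move together completely.

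The limit might or might not be crossed. Either way, a count of none or one tracing says little about the mean.

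**The case against.** Several points on the other side stand.

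- **The cardiac background is mild.** A reader might infer a known cardiac signal. The documents do not support that. Prolongation was seen at 250 mg/kg and not at 50 mg/kg, the in vitro studies were negative, and both Phase 1 studies, the second of which included 300 mg BID, reported no clinically relevant or meaningful ECG changes (A.1, A.2, H.2.1).
- **Nothing forbids an ECG table.** A reader might infer that a QTcF shift would go unreported. The SAP's list of laboratory measures is not worded as exhaustive, and K.2 points to a section that covers ECGs. What can be said is that no summary is planned.
- **Vital signs are not ignored.** Abnormal values are toxicity-graded, enter the AE tables and feed the study-level pausing rule in F.3.3.1. Only a group-level summary of the measurements is missing.
- **Individual risk is handled.** There are ECG entry criteria, central reading with investigator review, and stopping limits, and the PR and QRS limit uses averaged repeats rather than one tracing. The DSMB receives unblinded safety reports and the Medical Monitor looks for trends, though the documents do not say that either covers ECG data by treatment.
- **The 500 ms limit is not blind to a shift.** A reader might infer that a 10 ms shift would almost never show there. At the less favourable assumptions above, about one on-drug tracing is expected, and abnormalities below 500 ms can still become AEs.
- **A pooled mean has limits.** F.2.1 sets no ECG time relative to dose, so a peak effect could be missed.

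None of this provides a by-treatment estimate. Aim 1 is deliberately descriptive, and an estimate with a confidence interval and no test fits that.

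**Conclusion.** The gap is real and moderate. SAP Section 8 has no planned group-level summary of QTcF, PR, QRS or heart rate, and none of vital signs beyond graded AEs. The written routes for ECG findings work patient by patient and cannot estimate a mean QTcF shift, although safety is a primary objective and the crossover provides within-patient comparisons. Under the assumed SDs, with 29 completers, a QTcF difference could be estimated to within about 2.1 to 3.9 ms, or 2.9 to 5.5 ms from end-of-period ECGs alone. A 10 ms shift exceeds even the widest of these half-widths. The absence of planned text does not depend on any assumption; the precision figures depend on the assumed SDs and on independence of repeat ECGs.

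**What to change.** In SAP Section 8, before unblinding, add by treatment taken up to the visit:

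1. Descriptive summaries, observed and change from Baseline, of QTcF, PR, QRS, heart rate, pulse and blood pressure.
2. For QTcF at least, a drug-minus-placebo mean difference with 95% CI from the crossover mixed model already specified, with the Baseline value as a covariate and no hypothesis test.
3. Counts of patients in drug and in placebo periods who reach each ECG limit already in the protocol. No new limit is needed.
4. A stated limitation that ECG timing relative to dose is not controlled.

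In Protocol K.2, Aim 1, widen the sentence to laboratory, ECG and vital-sign measures so that the two documents agree.

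The cost is SAP and protocol wording, one or a few model fits, and some tables on data already being collected. There are no added visits or patients and no change to clinical management.
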